5.1 Duration of Study Participation

Patients' clinical outcomes will be monitored through EHR data for 18 months.

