Title	BETTER CARE – HF: Building Electronic Tools To Enhance and Reinforce Cardiovascular Recommendations – Heart Failure
Short Title	BETTER CARE – HF: Building Electronic Tools To Enhance and Reinforce Cardiovascular Recommendations – Heart Failure
Brief Summary	This study will test two types of electronic health record (EHR)-based alerts to improve guideline-adherent care for patients with heart failure and reduced ejection fraction (HFrEF). Alerts will be triggered for patients with ejection fraction (EF) \leq 40% who are not on guideline-recommended medical therapy. The two types of alerts tested will be a Best Practice Alert (BPA) and an electronic message.
Objectives	To test two types of EHR-based alerts that promote appropriate medical therapy for patients with HFrEF.
Methodology	Prospective cohort study
Endpoints	Primary endpoint: medication prescribing patterns Secondary endpoint: hospitalization and mortality
Study Duration	Eighteen months
Participant Duration	Eighteen months
Population	Patients with EF \leq 40%
Study Sites	One single health system, NYULH, consists of approximately 60 outpatient cardiology practices.
Number of participants	Up to 2000 participants
Statistical Analysis	We will begin all analyses with descriptive summary statistics and graphical displays of all variables. Primary analyses will utilize McNemar's tests for medication prescriptions and patient outcomes of hospitalization and mortality. We will adjust for patient demographics and clinical characteristics, as well as provider-level characteristics, such as demographics, panel size, insurance mix, and sub-specialty training.

CONFIDENTIAL

This material is the property of the NYU School of Medicine and Langone Medical Center. Do not disclose or use except as authorized in writing by the study sponsor

Schematic of Study Design

CONFIDENTIAL

This material is the property of the NYU School of Medicine and Langone Health. Do not disclose or use except as authorized in writing by the study sponsor

1 Introduction, Background Information and Scientific Rationale

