3.3 Study Endpoints

Outcomes measured at the prescription encounter level include whether there is a prescription for BB, ACE-I/ARB/ARNI, and/or MRA. Secondary patient outcomes include hospitalization, hospitalization for HF, and mortality.

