4.2 Inclusion Criteria

- Patient with an encounter visit at NYULH cardiology practice during the study period
- Patient with EF \leq 40% on most recent echocardiogram
- Patient ages 18-100

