4.4 Vulnerable Subjects

No vulnerable patients will be enrolled.

For the survey, we will recruit NYULH cardiologists who received the BPAs or messages. The only way to obtain feedback on the BPAs and electronic messages is from the cardiologists at NYULH who received the BPAs and electronic messages, as they are the only ones who can comment on the acceptability, usefulness, and ease of use of these EHR tools. Cardiologists will be informed that their decision to participate or not, and their responses, will in no way affect their employment, salary, or performance evaluations and they will be reminded that they can stop participating whenever they want. Their information will be de-identified and completely anonymous. No identifiable PII or health information will be collected.

5 Strategies for Recruitment

Eligible patients from the chosen practice sites will be identified electronically within EPIC using an algorithm developed by the study team and NYULH's DataCore. This algorithm reviews patient records for $EF \leq 40\%$ on most recent echocardiogram, and exclusion criteria listed above. Patients meeting eligibility will be automatically included, and all data collection will take place passively via the NYULH EHR system, EPIC. An EPIC reporting analyst will extract the relevant parameters from EPIC into a report. Patients from the selected practice sites will undergo their usual interactions with their providers and no study-specific activities will take place.

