5.2 Participant Withdrawal or Termination

Not applicable as the subjects are recruited at the clinic level.

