5.3 Provider Survey Recruitment

For the provider survey, we will recruit cardiologists who received the BPA or electronic message through emails (see attachment). They will be made aware that completing the survey is completely anonymous and will in no way impact their employment. The recruitment emails will be sent via listservs of cardiologist who received the BPAs and electronic messages. These listservs are specific for those cardiologists who received BPAs or electronic messages and the survey does not require cardiologists to self-select whether they received a BPA or a message. Only cardiologists who received a BPA or electronic message will be contacted. We will send an initial recruitment email and a subsequent follow up email.

The consent form will be attached to the email. It will also be available via link within the first question in Qaltrix. The first question in Qaltrix asks the provider to review the consent document and requires the provider to click a button stating that they are consenting to participate before being shown the remaining survey questions. If the provider does not click this button, they will not be able to move forward or complete the survey.

6 Study Schedule

Participants will be included in this study by virtue of meeting eligibility criteria and having a patient encounter during the study period. There are no study-specific visits. Any patient meeting criteria who has one or more patient encounters during the study period will be included. Therefore, no study-specific visits are relevant for this study, so there is no schedule of visits.

CONFIDENTIAL

This material is the property of the NYU School of Medicine and Langone Health. Do not disclose or use except as authorized in writing by the study sponsor

7 Study Procedures / Evaluations

There are no study-specific procedures that patients will undergo. They will receive care as usual by their outpatient providers. The EHR algorithm developed by the study team identifies eligible patients with EF \leq 40% on most recent echocardiogram, and exclusion criteria listed above. The EHR algorithm will also capture information on demographics, diagnoses in the patient's problem list, prescription history, allergies, EF, and relevant lab results.

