For patients meeting the eligibility criteria, a message in the EHR will automatically be sent to the provider. The provider will receive either a Best Practice Alert (BPA) or electronic message indicating that their heart failure patient is not on guideline-recommended therapy. The message will offer guidance for physician decision-making regarding HFrEF care. The study team presented the proposed project to the NYULH MCIT Project Portfolio Review Committee on February 11, 2021 and was approved to work with MCIT to build the electronic messages. Providers will be notified through the Weekly Epic Update and in presentations to medical directors that they may see the alert prior to the start of the study.

Patients' clinical outcomes will be monitored through EHR data collection for 18 months. Data collection will include elements of protected health information including patient name, medical record number, address zip code, and service dates. These will be necessary for data linkages and in order to track patients for receipt of intervention and clinical outcomes. All PHI data will be kept on a secure NYULH server and destroyed at the earliest possible point. Data on the patient's medication prescription, hospitalization, hospitalization for HF, and mortality will be recorded as study outcomes. The study team members will not collect this information directly; data will be collected in NYULH's EHR system, EPIC, and an EPIC Reporting analyst from DataCore will extract the relevant parameters from the EHR into a report.

Data points that will be collected for research purposes
Medication prescription
Hospitalization
Hospitalization for HF
Mortality
Name
Medical record number
Address zip code
Service dates

Provider survey data will be anonymously collected via Qualtrix. No identifiable information, PII, or health information will be collected. The URLs for the survey are below:

BPA version = https://nyumc.yul1.qualtrics.com/jfe/preview/previewId/f42fb1cb-b997-4fb8-8f60-9e311e6b6320/SV_7P3UhfVSH6KgpuK?Q_CHL=preview&Q_SurveyVersionID=current

IBM version = https://nyumc.yul1.qualtrics.com/jfe/preview/previewId/c97ab951-3feb-478a-8af8-a53e9abbe02d/SV_7PQoQunPLM8I8ZU?Q_CHL=preview&Q_SurveyVersionID=current

8 Safety and Adverse Events

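### Study duration and participant duration are both 18 months although patients enter at any encounter, and the test planned for hospitalization and mortality needs pairs and takes no account of time at risk

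*Combined protocol and SAP*

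**What the plan says.** **Duration.** The Protocol Summary has separate rows for study duration and participant duration, and both read "Eighteen months". Section 5.1 states that patients' "clinical outcomes will be monitored through EHR data for 18 months". Section 7 repeats that "clinical outcomes will be monitored through EHR data collection for 18 months". Neither section says from what date the 18 months run.

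**Entry.** Section 4.2 requires a "Patient with an encounter visit at NYULH cardiology practice during the study period". Section 6 adds: "Any patient meeting criteria who has one or more patient encounters during the study period will be included". Under section 5, "Patients meeting eligibility will be automatically included". The visible text gives no last entry date, index date or data cut-off. The study schematic is not shown in the text available.

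**Analysis.** Section 3.3: "Secondary patient outcomes include hospitalization, hospitalization for HF, and mortality". The Protocol Summary and section 9.3 assign McNemar's test to prescribing, hospitalization and mortality. Both also promise adjustment for patient and provider characteristics. They name no model for this, and follow-up time is not among the listed covariates. Section 9.2 plans three arms of 501. Section 5.2 treats withdrawal as not applicable because "the subjects are recruited at the clinic level", and no censoring rule appears elsewhere.

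**The concern.** A patient who first qualifies in month 10 of an 18-month study has at most 8 months of follow-up from that encounter. The two summary rows therefore conflict for every patient who does not enter at the start, and the remedy depends on which row is meant.

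The planned test makes this matter. McNemar's test compares two yes/no results within matched pairs. The plan describes no pairs for these outcomes, and a patient followed for one month without an event counts the same as one followed for 18 months without an event. If follow-up varies, the reported proportion with a hospitalization or death depends on when patients happened to enter, and it cannot be read as a risk over a stated period. The plan also does not say how to count a patient who dies before any hospitalization.

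**Working it through.** The plan gives no event rate or power figure for hospitalization or mortality, so there is no figure of its own to reproduce here. The check has three steps.

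**1. Can both durations hold?** Let patients enter over the first w months.

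- If each patient is followed for 18 months from entry, the study lasts 18 + w months. For w = 6, 12 or 18 that is 24, 30 or 36 months, against a stated 18.
- If the study ends at 18 months, follow-up from entry runs from 18 − w to 18 months. With uniform entry its mean is 18 − w/2, which is 15, 12 or 9 months.

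Both rows hold for follow-up from entry only when w = 0.

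**2. What would a yes/no proportion estimate if 18 months is the calendar length?** The documents give only the 18 months. The rest is assumed: uniform entry over w months, a constant hazard, and a true 18-month risk R of 20% (range 10% to 30%).

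- Hazard: L = −ln(1 − R)/18. For R = 20%, L = 0.22314/18 = 0.012397 per month.
- Expected observed proportion, with a = 18 − w: 1 − [exp(−La) − exp(−18L)]/(Lw).

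For R = 20%:

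- w = 6: 1 − (0.86177 − 0.80000)/0.07438 = 17.0%
- w = 12: 1 − (0.92832 − 0.80000)/0.14876 = 13.7%
- w = 18: 1 − (1.00000 − 0.80000)/0.22314 = 10.4%

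| Entry over first | Mean follow-up | R = 10% | R = 20% | R = 30% |
|---|---|---|---|---|
| 6 months | 15 months | 8.4% | 17.0% | 25.7% |
| 12 months | 12 months | 6.8% | 13.7% | 21.0% |
| 18 months | 9 months | 5.1% | 10.4% | 15.9% |

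With entry throughout the study, the reported figure is about half the 18-month risk.

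**3. What would a common fixed window cost under the calendar reading?** The share of patients who can complete t months is min(1, (18 − t)/w). Of the 1503 patients in section 9.2:

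- t = 12: none lost for w = 6; half, about 751, for w = 12; two thirds, 1002, for w = 18.
- t = 6: none lost for w = 6 or 12; one third, 501, for w = 18.

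**The case against.** **The per-patient reading is the more natural one.** Section 5.1 is headed as participation and the summary has its own participant row. On that reading a yes/no outcome at 18 months is a proper fixed window, and only the study-duration row needs correcting. This stands as far as time at risk goes. It does not rescue McNemar's test, because the comparison is between arms and no pairs are described.

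**One calendar window for the whole cohort would fit both rows.** Sections 4.2 and 6 define who is included, not when the outcome clock starts, and the missing schematic may show the windows. This also stands, so the two rows are not irreconcilable. But time at risk after the index encounter would then vary, and the test would still ignore it.

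**The promised adjustment implies some model beyond a bare McNemar test.** Perhaps so, but none is named and follow-up time is not listed.

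**The stakes are limited.** The outcomes are secondary, the sample size is set for prescribing, and the study is described and funded as a pilot. That limits the weight of the point but does not remove it.

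**A stronger reading is tempting.** A reader might infer that unequal follow-up biases the comparison between arms or inflates its false-positive rate. That needs follow-up to differ by arm. Inclusion is automatic and encounter-based, with no reference to arm, so the documents give no reason to expect a difference. With the same follow-up distribution in every arm, this distortion does not arise.

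**Conclusion.** The point holds in a limited form and should be corrected before these outcomes are analysed. Follow-up of 18 months from entry, an 18-month study and entry at any encounter cannot all hold unless everyone enters at the start. The plan does not say which 18 months it means. McNemar's test does not suit a comparison between arms without defined pairs, whichever reading applies.

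If 18 months is the calendar length, the reported proportion understates the 18-month risk. At an assumed 20% risk it would be about 17%, 14% or 10% for entry over 6, 12 or 18 months. These sizes rest on assumed uniform entry, a constant hazard and assumed risks; none of these is in the documents. If every patient has 18 months of follow-up, this understatement disappears, and what remains is the stated study length and the choice of test. The calculation concerns the absolute risk reported, not the difference between arms.

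**What to change.** **Reconcile the Protocol Summary with sections 4.2, 5.1, 6 and 7.** State whether 18 months is the study length or each patient's follow-up. Give the entry window and the data cut-off. Define one index date in the same way for all three arms, for example the first eligible encounter after go-live, whether or not an alert was shown.

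**In section 9.3, replace McNemar's test for hospitalization, HF hospitalization and mortality:**

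- If 18 months is the calendar length, analyse time from index date to event, censored at the cut-off, with death as a competing event for the two hospitalization outcomes. This keeps every patient.
- If every patient does have 18 months, use an unpaired between-arm model for the binary outcome over that window, with a stated rule for death before hospitalization.
- In either case use standard errors that allow for clustering by clinic, since section 5.2 places recruitment at that level.

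**Cost.** Some wording changes and a little more analysis work. Section 7 lists the outcomes and service dates but no separate date of death, so the sponsor should confirm that dates of death and of admission are extracted. A fixed window has a further price under the calendar reading, because it drops late entrants in the numbers shown in step 3.

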5.2 Participant Withdrawal or Termination

Not applicable as the subjects are recruited at the clinic level.

5.3 Provider Survey Recruitment

For the provider survey, we will recruit cardiologists who received the BPA or electronic message through emails (see attachment). They will be made aware that completing the survey is completely anonymous and will in no way impact their employment. The recruitment emails will be sent via listservs of cardiologist who received the BPAs and electronic messages. These listservs are specific for those cardiologists who received BPAs or electronic messages and the survey does not require cardiologists to self-select whether they received a BPA or a message. Only cardiologists who received a BPA or electronic message will be contacted. We will send an initial recruitment email and a subsequent follow up email.

The consent form will be attached to the email. It will also be available via link within the first question in Qaltrix. The first question in Qaltrix asks the provider to review the consent document and requires the provider to click a button stating that they are consenting to participate before being shown the remaining survey questions. If the provider does not click this button, they will not be able to move forward or complete the survey.

6 Study Schedule

Participants will be included in this study by virtue of meeting eligibility criteria and having a patient encounter during the study period. There are no study-specific visits. Any patient meeting criteria who has one or more patient encounters during the study period will be included. Therefore, no study-specific visits are relevant for this study, so there is no schedule of visits.

CONFIDENTIAL

This material is the property of the NYU School of Medicine and Langone Health. Do not disclose or use except as authorized in writing by the study sponsor

7 Study Procedures / Evaluations

There are no study-specific procedures that patients will undergo. They will receive care as usual by their outpatient providers. The EHR algorithm developed by the study team identifies eligible patients with EF \leq 40% on most recent echocardiogram, and exclusion criteria listed above. The EHR algorithm will also capture information on demographics, diagnoses in the patient's problem list, prescription history, allergies, EF, and relevant lab results.

For patients meeting the eligibility criteria, a message in the EHR will automatically be sent to the provider. The provider will receive either a Best Practice Alert (BPA) or electronic message indicating that their heart failure patient is not on guideline-recommended therapy. The message will offer guidance for physician decision-making regarding HFrEF care. The study team presented the proposed project to the NYULH MCIT Project Portfolio Review Committee on February 11, 2021 and was approved to work with MCIT to build the electronic messages. Providers will be notified through the Weekly Epic Update and in presentations to medical directors that they may see the alert prior to the start of the study.

Patients' clinical outcomes will be monitored through EHR data collection for 18 months. Data collection will include elements of protected health information including patient name, medical record number, address zip code, and service dates. These will be necessary for data linkages and in order to track patients for receipt of intervention and clinical outcomes. All PHI data will be kept on a secure NYULH server and destroyed at the earliest possible point. Data on the patient's medication prescription, hospitalization, hospitalization for HF, and mortality will be recorded as study outcomes. The study team members will not collect this information directly; data will be collected in NYULH's EHR system, EPIC, and an EPIC Reporting analyst from DataCore will extract the relevant parameters from the EHR into a report.

Data points that will be collected for research purposes
Medication prescription
Hospitalization
Hospitalization for HF
Mortality
Name
Medical record number
Address zip code
Service dates

Provider survey data will be anonymously collected via Qualtrix. No identifiable information, PII, or health information will be collected. The URLs for the survey are below:

BPA version = https://nyumc.yul1.qualtrics.com/jfe/preview/previewId/f42fb1cb-b997-4fb8-8f60-9e311e6b6320/SV_7P3UhfVSH6KgpuK?Q_CHL=preview&Q_SurveyVersionID=current

IBM version = https://nyumc.yul1.qualtrics.com/jfe/preview/previewId/c97ab951-3feb-478a-8af8-a53e9abbe02d/SV_7PQoQunPLM8I8ZU?Q_CHL=preview&Q_SurveyVersionID=current

8 Safety and Adverse Events

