9.1 Study Hypotheses

Patient in clinics receiving the EHR-based alerts will have higher rates of adherence to guideline recommended medical therapy.

Providers will like the EHR-based alerts and will want to continue to use them in their practice.

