9.2 Sample Size Determination

In order to have 80% power to detect a 10% improvement in prescribing for each intervention arm vs. control, we will require a total of at least 1503 patients (501 per arm). Based on prior data, we estimate that alerts will trigger for a sample between 1500-2000 patients, but are unable to accurately control the specific number of patients due to fluctuating clinical volume at practices.

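### Section 9.2 powers each alert against a control arm of 501, but Section 7 carves out no control practices, no readable section defines the control or its assignment, and McNemar's test does not fit independent arms

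*Combined protocol and SAP*

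**What the plan says.** **Sample size (9.2).** The 80% power is "for each intervention arm vs. control, we will require a total of at least 1503 patients (501 per arm"). The same section adds that "we estimate that alerts will trigger for a sample between 1500-2000 patients".

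**Delivery (Section 7).** "For patients meeting the eligibility criteria, a message in the EHR will automatically be sent to the provider". The next sentence reads: "The provider will receive either a Best Practice Alert (BPA) or electronic message". Neither sentence mentions practices where the alert is withheld.

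**Design and intervention (3.1, 3.2).** Section 3.1 describes where the ambulatory sites are and which EHR they use. Section 3.2 describes the two alert types. Neither describes a control condition. The Methodology entry in the Protocol Summary labels the study a prospective cohort.

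**Hints of a comparator.** Section 9.1: "Patient in clinics receiving the EHR-based alerts will have higher rates of adherence". Section 5: "Eligible patients from the chosen practice sites will be identified electronically". Section 5.2, on withdrawal: "Not applicable as the subjects are recruited at the clinic level". Section 5.3, on the survey: "Only cardiologists who received a BPA or electronic message will be contacted".

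**Analysis (9.3).** McNemar's test is primary for prescriptions, hospitalization and mortality, with adjustment for patient and provider characteristics.

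**The concern.** The sample size section and the delivery section do not describe the same study. One needs a control group of 501. The other, as worded, routes patients who meet eligibility to one of two alerts.

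Three things depend on the answer. The EHR build needs to know where to suppress the display and whether to go on logging patients there. The analyst needs to know who the controls are, and whether they are concurrent practices, earlier patients, or the same patients before the alert. The reader of the results needs to know whether practices were randomized or picked, because picked practices may already differ in prescribing.

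The named test does not settle the matter. A paired test suggests before-after or matched data, while a size per arm suggests parallel groups.

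**Working it through.** **1. The plan's own figure.** Section 9.2 gives 1503 in total and 501 per arm. 1503 / 501 = 3. Two alert types are described in 3.2, so the third group is the control that 9.2 names, with 501 patients.

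**2. Section 7 taken literally.** The same 1503 patients would fall into two alert groups, 1503 / 2 = 751.5 or about 751 each if equal, with no concurrent unalerted patients. The concurrent contrast left would be BPA versus message, which 9.2 does not power and 9.1 does not hypothesize.

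**3. What the 1500-2000 counts.** Section 9.2 says alerts trigger for this many patients. There are two readings:

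- *All arms:* 1500 / 3 = 500 and 2000 / 3 = 667 per arm. Two alert arms then hold about 1000 to 1333 patients and the control about 500 to 667. This is in line with the 501 planned, one patient per arm short at the low end.
- *Alerted patients only:* even the low end plus the planned control gives 1500 + 501 = 2001, and the high end gives 2000 + 501 = 2501. The Protocol Summary allows up to 2000 participants.

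The all-arms reading fits the plan's other figures better, but the text does not state it.

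**4. The test.** McNemar's statistic is (b - c)² / (b + c), where b and c count the two kinds of discordant pair. Patients in separate arms form no pairs, and no section describes matching. Pairing each patient with his or her own earlier status is conceivable for prescriptions. It cannot work for mortality, because nobody enters the study already dead. The test also takes no covariates, although 9.3 plans to adjust for them.

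**5. Clustering, for illustration.** The Protocol Summary gives about 60 practices. If all took part equally, 1503 / 60 = 25.05 patients each, and the design effect is 1 + 24.05 x ICC. The documents give no ICC, so these values are assumptions:

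| Assumed ICC | Design effect | 501 / design effect |
|---|---|---|
| 0.01 | 1.24 | 404 |
| 0.02 | 1.48 | 338 |
| 0.05 | 2.20 | 227 |

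Section 9.2 does not say whether 501 already allows for this. The table shows only why the analysis has to respect practice; it does not show that the study is underpowered.

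**The case against.** The strongest reply is that a control is plainly part of the plan. Section 9.2 names it. Section 9.1 contrasts clinics that receive alerts with, by implication, clinics that do not. Section 5.3 limits the survey to cardiologists who received one. Section 7 itself says providers will be warned that an alert might appear, and that identifiers are kept partly to track who received the intervention. The schematic is a natural place to show arms and allocation, and its absence from the text available here is not a fault in the plan. All of this stands, and it means that the control is undefined rather than absent.

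Two stronger readings are tempting, and the documents support neither.

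- *Every eligible patient triggers an alert, so there is no control.* Section 7's sentence cannot be an exact universal rule. The criteria in 4.2 and 4.3 do not require a treatment gap, while the Protocol Summary and Section 7 tie the alert to patients who have one. It reads as a loose account of how the tool works. Nor does 3.4 decide the matter: its reference to all cardiology locations may attach to the surveys, to a later roll-out, or to sites carrying different arms.
- *Neither powered contrast could be estimated.* A pre-alert or historical control would still permit an estimate, though a weaker one, exposed to secular change in prescribing. The cohort label and the paired test leave that possibility open.

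What the reply does not answer is that the sections where the control condition and the assignment rule belong (3.1, 3.2, 5 and 7) are readable and contain neither. A figure would not remove the contrary wording in Section 7.

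**Conclusion.** The point holds as a conflict of wording with practical consequences. Section 9.2 requires 501 control patients. Section 7 makes no exception for them, and no readable section says what control practices experience, whether the control is concurrent, or how practices are assigned.

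Followed literally, Section 7 would leave no concurrent untreated comparator for the two contrasts that 9.2 powers. That is the worst case, not the likely intent. Separately, McNemar's test does not suit the independent arms in 9.2 whatever the schematic shows, unless a pairing is defined that the text does not mention.

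Confidence is moderate. The mismatch between sections is certain from the text; the intended design is not, because the schematic cannot be seen. The figure of about 500-667 per arm assumes three equal arms and the all-arms reading of 1500-2000.

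**What to change.** 1. **Section 7.** State that the allocated alert is displayed only in practices assigned to BPA or to message. In control practices the same algorithm runs silently, logs patients who meet the same trigger criteria, and outcomes are extracted in the same way.
2. **Section 9.2.** If this is what is meant, say that the 1500-2000 are patients meeting the trigger criteria across all arms, about 500-667 per arm.
3. **Section 3.1 and Methodology.** State the allocation unit and method, consistently with the schematic, and make the design label match. If practices are not randomized, say how they are chosen and describe the study as a non-randomized comparison.
4. **Section 9.3.** Replace McNemar's test with a comparison of independent arms by allocated practice that accounts for clustering, such as a mixed or GEE logistic model with the covariates already planned.

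The cost is protocol wording, an allocation list, and practice-level display switches with silent logging in the EHR build. The logging rule should be set before go-live, since recording controls identically at the moment of trigger may be hard to recover later. The 80% power may need restating with the alpha, control rate and ICC actually used, none of which 9.2 gives.
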